8.6. Study Drug Accountability and Reconciliation

All patients will be expected to bring their bottles of study medication with them to all study visits. The site staff will inspect the medication bottles, perform a count of the tablets remaining in the bottles, and document this in the patient's record. An assessment of medication adherence should be done by the study staff to ensure that the patient understands all dosing instructions and is taking the medication as prescribed. If it is found that the patient is not taking the study medication as prescribed, the patient will be re-c counseled on correct administration, and this should be noted in the patients' records, and discussed with the medical monitor if necessary.

All study medication, including partial and empty bottles, must be maintained at the study site until Tonix or its designee verifies drug accountability and provides instruction for the destruction or the return of the investigational product to the Sponsor's drug distribution depot.

Tonix or their designee will perform drug accountability which entails reconciliation between the amount of drug shipped to the study site, study drug assigned and dispensed to the patient (including returned unused assigned study drug), and study supplies that were never dispensed and/or assigned to patients.

9. STUDY VISITS AND PROCEDURES

The overall and detailed schedule for study procedures and visits is provided in [Appendix 1](#).

9.1. Visit 1 – Screening/Baseline (Week 0, Day 1)

9.1.1. Informed Consent

Before the potential patient has undergone any study-related screening procedures, the nature of the study and the potential risks associated with it will be explained to the patient, and the patient will be given an opportunity to ask questions to his or her satisfaction. After all questions are answered, but before proceeding further, the patient must read and sign a written informed consent form. This signed informed consent form will be retained in the Investigator's study file, and the date the patient signed the form will be entered into the Case Report Form (CRF). The patient will be provided with a copy of his or her signed and dated informed consent form. The patient will be required to sign all updated informed consents.

9.1.2. Screening Overview

The first study visit, Visit 1, will be where the study is explained to the prospective study patient, where written informed consent will be obtained and documented, and where protocol-specified study procedures and assessments will be completed. This visit date is intended to be the same date as the final primary outcome endpoint of the lead-in study (Week 12); however, if there are extenuating circumstances, Visit 1 of P303 may occur within fourteen days of completion of the lead-in study without repeating baseline assessments. If more than fourteen days elapse between the final visit of the lead-in study and start of the P303 study, baseline assessments will need to be repeated.

Once the patient has provided written informed consent to participate and has met all relevant inclusion criteria, this patient is eligible to begin the open-label treatment period starting at bedtime. The patient should be dispensed two bottles of TNX-102 SL tablets, along with instructions on usage. The end-of-study information collected in the double-blind lead-in study will be considered the baseline values for Study P303.

9.1.3. Patient Numbering

All patients who complete the double-blind lead-in study will retain their original concatenated 6-digit site-patient number. A log documenting the following information will be recorded and maintained at the study site: patient's initials, 6-digit identification number, and whether or not the patient met inclusion criteria and received open-label study medication. If the patient did not meet these requirements, then the reason(s) for exclusion from the study should be documented.

9.1.4. Visit 1 Baseline Assessments/Procedures (Week 0)

The following assessments/procedures will be completed at Visit 1. If assessments were collected as part of the final visit for the double-blind lead-in study, they will not need to be repeated.

- Obtain written informed consent to participate
- Inclusion criteria

- Review and transcribe new concomitant medications as well as those which are to be continued from the final visit of the double-blind lead-in study
- Review and transcribe new AEs as well as those which are ongoing from the final visit of the double-blind lead-in study
- Review findings obtained at the final visit of the double-blind lead-in study, including visual exam of the oral cavity, vital signs, and weight. The height collected at baseline from the lead-in study will be utilized for BMI calculations in this study.
- Review results of the Beck Depression Inventory (BDI-II) and Columbia-Suicide Severity Rating Scale (C-SSRS) completed at the final visit of the double-blind lead-in study.
- Review all clinical laboratory test results obtained at the final visit of the double-blind lead-in study within 7 days of their release from the central lab (serum chemistries, hematology). Confirm negative urine pregnancy test (for women of child-bearing potential) obtained at the final visit of the double-blind lead-in study.
- Review patient's lifetime psychiatric treatment history, demographic information and medical history to ensure the information recorded during the double-blind lead-in study is accurate and complete, as it will also be included in the extension study's database.
- The following assessments were completed as part of the final visit of the double-blind lead-in study: CAPS-5, PROMIS, and SDS.

Only those patients meeting all of the inclusion criteria will be eligible to continue. After all study requirements for Visit 1 of P303 have been fulfilled, the patient will:

- Be dispensed two bottles of TNX-102 SL tablets and be instructed to begin dosing with study medication at bedtime, starting the evening of Visit 1;
- Receive instruction regarding proper sublingual dosing technique and the time of expected dosing; and
- Schedule the telephone visit 2 and receive an appointment to return to the clinic for Visit 3.

9.2. Visit 2 (Telephone Visit: Week 2)

Visit 2 will be done as a telephone call to the patient and should be conducted after 2 weeks of treatment, on Day 14 ± 3 days.

The following steps should be completed:

- Assess changes in concomitant medications
- Assess study drug compliance based on patient verbal report
- Assess occurrence of adverse events, including any oral adverse events and whether an unscheduled visit is indicated for an examination of the oral cavity
- Review patient instructions regarding drug dosing

- Administer the 'Since Last Visit' C-SSRS telephonically

9.3. Visits 3 and 4 (Weeks 4 and 8)

These visits are conducted after 4 and 8 weeks (28 ± 7 and 56 ± 7 days) of treatment respectively. The following assessments and procedures are to be conducted at each of these visits in the following general order:

- Assess for occurrence of AEs
- Perform and document an examination of the oral cavity if any oral AEs have been reported
- Assess for changes in concomitant medications
- Patient scales
 - BDI-II
- Clinician Administered Scales
 - C-SSRS
 - CGI-I considering both baselines
- Vital signs and weight
- Urine pregnancy test (for women of child-bearing potential)
- Collect returned study medication from patient
- Perform drug accountability
- Assess study drug compliance
- Dispense 2 new bottles of TNX-102 SL tablets

Review patient instructions regarding drug dosing and schedule appointment for next clinic visit.

9.4. Visit 5 (Week 12)

Visit 5 is to be conducted after 12 weeks (84 ± 7 days) of treatment in the extension study. At this visit, the patient will return all remaining study drug and the following assessments and procedures are to be completed in the following general order:

- Assess for occurrence of AEs
- Assess for changes in concomitant medications
- Patient scales
 - BDI-II
 - SDS
 - PROMIS sleep disturbance
- Clinician Administered Scales
 - C-SSRS

- CAPS-5
- CGI-I considering both baselines
- Vital signs and weight
- Visual inspection of the oral cavity
- Clinical laboratory tests
- Urine pregnancy test (for women of child-bearing potential)
- Assess and document study drug compliance

9.5. Early Termination (ET)

In accordance with the Declaration of Helsinki, patients have the right to withdraw from the study at any time for any reason, and they will be advised of this right. The investigator and Tonix also have the right to remove patients from the study. Specific reasons for removal of a patient from the study could include, but are not limited to:

- An adverse event (AE)
- An illness that, in the judgment of the investigator or Tonix, might invalidate the study results or place the patient at risk
- The request of the patient, investigator, or Tonix, whether for administrative or other reasons
- Pregnancy

Patients who wish to terminate their participation in the study should be instructed to come to the clinic for an Early Termination Visit. The purpose of the Early Termination visit is to obtain critical information about the patient's participation, and should be scheduled preferably before there has been a substantial lapse in study medication usage. However, even if there has been a medication lapse, the patient should be encouraged to return to the clinic for this visit, and should be instructed to return all remaining study medication.

The following assessments and procedures are completed at this visit in the following general order:

- Assess for occurrence of AEs
- Assess for changes in concomitant medications
- Patient scales
 - BDI-II
 - SDS
 - PROMIS sleep disturbance
- Clinician Administered Scales
 - C-SSRS
 - CAPS-5
 - CGI-I considering both baselines

- Vital signs and weight
- Visual inspection of the oral cavity
- Clinical laboratory tests
- Urine pregnancy test (for women of child-bearing potential)
- Assess and document study drug compliance

Once these assessments have been completed, the patient may be discharged from the study, provided there is no need for additional follow-up to continue to monitor an adverse event or other condition.

9.6. Unscheduled Visits

Patients may need to be seen at other times than the scheduled study visits for additional safety assessments or to follow-up, as medically necessary, on clinical laboratory, physical examination, or other findings. In addition, if a patient calls between scheduled visits to report a visible lesion in the oral cavity or other concerning oral cavity AE, the patient should be asked to return to the clinic as soon as possible for an unscheduled oral cavity examination. If an additional study visit occurs, the date and nature of the visit will be documented in the CRF and in the source documents.

10. STUDY ASSESSMENTS

10.1. Screening Assessments

Most screening assessments will be completed as part of the Week 12 visit of the lead-in study, as outlined in [Section 9.1.4](#). The results of these assessments should be reviewed to ensure that the patient continues to satisfy all entry criteria and otherwise remains a satisfactory patient for the extension study. Laboratory assessments obtained at the final visit of the double-blind lead-in study will not be available prior to the patient's entry into the extension study, but should be reviewed within 7 days when they become available, to ensure the patient's ongoing well-being.

10.2. Efficacy Assessments

The assessment of efficacy is a secondary objective of this study and these endpoints are derived from both clinician-administered and subjective patient-completed assessments. The clinician-administered assessments must be administered by qualified and trained individuals at each clinical site. Study specific training will be required before new staff that were not trained for the lead-in study are allowed to administer these scales. In an attempt to minimize variability in responses of a given patient over time, it is important that the same rater administer the scales to a given patient throughout the study as much as possible. It is also important that the assessments, including those that are patient-completed, be conducted in the specified order, according to specific instructions, and in a setting where the patient has minimal distractions and sufficient time to complete them. After completion of these assessments, the study coordinator should review the responses for completeness with the patient.

NOTE: All of the assessments required for Visit 1 will come from the results at the final visit of the double-blind lead-in study as long as the patient enrolls within 14 days of the final visit of the double-blind lead-in study. Only if the timeframe is longer than 14 days would there be a need to repeat these assessments.

10.2.1. Clinician Administered PTSD Scale for DSM-5 (CAPS-5)

The CAPS-5 symptom severity 1-week recall version will be administered by qualified and trained clinicians at the final visit of the double-blind lead-in study and at the final clinic study visit (Weeks 12). In an attempt to minimize variability in the rating of CAPS-5 responses over time and between the lead-in and extension (P303) studies, as much as possible the same rater who performed the CAPS-5 throughout the lead-in study should also administer this assessment for the final visit in P303. Additional information regarding the conduct, rating, and scoring of the CAPS-5 instrument as well as the requirements for rater training will be provided separately.

10.2.2. Clinical Global Impression of Improvement (CGI-I)

The CGI-I is a commonly used clinician-rated scale designed to assess overall clinical improvement (change) since baseline, which for this study will be defined in two ways: (1) from the baseline visit of the lead-in double-blind study and (2) from the baseline visit of the extension study. The CGI-I will be completed at each clinic visit. It will be the responsibility of the Principal Investigator or his qualified designee to assess change in the subject's overall status from both baselines.

10.2.3. Sheehan Disability Scale (SDS)

The SDS scale is a self-report questionnaire that was designed to assess the subject's view of the degree to which symptoms have disrupted work, social life/ leisure activities, and family life/ home responsibilities during the past week. In addition, the SDS asks the subject to provide the number of days or work lost as well as unproductive days. The SDS will be administered at Baseline (Visit 1) and endpoint (Visit 5).

10.2.4. PROMIS Sleep Disturbance Scale

PROMIS refers to the Patient-Reported Outcome Measurement Information System (www.nihpromis.org), an NIH-funded initiative to develop instruments to be used across chronic conditions. The PROMIS Scale for sleep disturbance (form 8a) will be administered at Baseline (Visit 1) and endpoint (Visit 5).

10.2.5. Beck Depression Index (BDI-II)

BDI-II refers to the patient-rated assessments of depressive symptomology. The BDI-II will be administered at Baseline (Visit 1) and Visits 3, 4, and endpoint (Visit 5).

10.3. Safety Parameters

Safety will be assessed by evaluation of adverse events, responses on the C-SSRS, clinical laboratory tests, examinations of the oral cavity, vital signs, weight, and patient-rated assessments of depressive symptomology (BDI-II).

10.3.1. Adverse Events (AEs)

Patients will be monitored for AEs throughout the study, from the time the patient signs an informed consent onward. AEs that are spontaneously reported, elicited or observed are to be recorded on the CRF with the date, time of onset, date and time of resolution, severity, seriousness, causality (relationship to study medication), actions required, and outcome.

To elicit AEs, non-leading, simple questions with minimal connotations should be used as the initial questions at all evaluation points during the study. Examples of these questions can be:

- How have you felt since your last visit?
- Have you had any health problems since your last visit?

If an AE occurs, the investigator will institute support and/or treatment as deemed appropriate. If a non-serious AE is unresolved on the last day of the study, an effort should be made to follow up until the AE is resolved or stabilized, the patient is lost to follow-up, or there is some other resolution of the event.

There are many symptoms associated with PTSD that can vary in intensity and frequency over time. Only symptoms that significantly worsen or become more frequent, and in the opinion of the patient are outside of their normal experience, should be reported as adverse events.

If a patient reports an oral adverse event other than numbness, tingling or bitter taste, the Investigator should examine the oral cavity to confirm presence or absence of any lesion or other abnormality, and document the exam. Additional details related to onset, duration, severity and reversibility of the oral event will also be documented.

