Safety data will be summarized by treatment group. Adverse events will be coded using the same version of the Medical Dictionary for Regulatory Activities (MedDRA) as used for the lead-in study and will be summarized overall and by preferred term and system organ class (SOC). Adverse events will also be summarized by severity and relationship to study drug. Serious AEs and AEs leading to discontinuation of study drug will also be summarized. Adverse events that are ongoing at Week 12 from the lead-in study will be transcribed into the eCRF. All other adverse events that are reported after starting TNX-102 SL 5.6 mg in this extension study, or that worsen after entry into the extension study, will be considered newly emergent AEs (NEAEs), even if the type of event was previously reported (and resolved) during the lead-in study.

Actual values and changes from both baselines for clinical laboratory test results, vital sign measurements, and in the BDI-II score will be summarized at endpoint using descriptive statistics (n, mean, SD, median, minimum, and maximum). The number of patients with baseline and treatment-emergent suicidal ideation and/or suicidal behavior or self-injurious behavior, based on the C-SSRS, will be summarized by treatment group.

Efficacy Analyses:

Descriptive statistics by treatment group and study visit will be displayed for a number of efficacy endpoints, including:

- Change from both baselines in the total CAPS-5 score
- Proportion of patients with a CGI-I score of “very much improved” or “much improved” from both baselines
- Change from both baselines in the SDS total score
- Change from both baselines in the individual items assessed using the SDS
- Change from both baselines in patients’ quality of sleep using the PROMIS Sleep Disturbance scale
- Change from both baselines in CAPS-5 symptom cluster subscores
- Proportion of patients with a $\geq 50\%$ improvement from baseline (both baselines) in total CAPS-5 score
- Change from both baselines in BDI-II score

Hypothesis testing will also be performed on the above efficacy endpoints. Missing values will not be imputed, and no adjustments will be made for multiplicity.

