11. DEFINITIONS, RECORDING, AND REPORTING OF ADVERSE EVENTS AND PREGNANCY

11.1. Definition of Adverse Events

According to International Conference on Harmonisation (ICH) guidance E2A, Clinical Safety Data Management: Definitions and Standards for Expedited Reporting, an adverse event (AE) is any untoward medical occurrence in a patient or clinical investigation patient administered a pharmaceutical product and which is not necessarily required to have a causal relationship with this treatment. An AE can therefore be any unfavorable and unintended sign (including an abnormal laboratory finding, for example), symptom, or disease temporally associated with the use of a medicinal product, whether or not considered related to the medicinal product.

A newly-emergent adverse event (NEAE) is defined as any new AE that starts after the patient's baseline visit for P303, or any ongoing AE that was first reported during the lead-in study and which then exhibits an increase in severity, frequency or relationship after the patient's participation in P303 has begun. NEAEs and "All AEs" will be tallied by SOCs and preferred terms. Adverse events that are ongoing at the time of the patient's baseline visit for P303 but which resolve, or persist without change in severity, frequency or relationship to study drug during the extension study, will be included in the tally of All AEs.

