9.1.1 Efficacy Analysis Model

Continuous endpoints collected at baseline and Week 12 will be analyzed in an analysis of covariance model (ANCOVA) for the change from each baseline (P301 baseline and P303 baseline) in separate, independent models. The model will include all participants in the safety population, and the dependent variable will be the observed change from each baseline to Week 12. Covariates in the model will include the fixed categorical effects of treatment, site, sex, current tobacco use status, presence of current MDE, as well as the continuous fixed covariate of baseline score.

The least squares means and 95% confidence intervals (CIs) will be calculated for the treatment difference between the subjects that received TNX-102 SL and placebo in the lead-in study at each time point.

Endpoints reported in this manner will include:

- CAPS-5 Total Score
- Change from baseline in SDS total.
- Change from baseline in participants' quality of sleep using the PROMIS Sleep Disturbance scale.
- Change from baseline in the disruption of work/school activities assessed using the SDS.
- Change from baseline in disruption of social life/ leisure activities assessed using the SDS.
- Change from baseline in the disruption of family life/home responsibilities assessed using the SDS.
- Change from baseline in CAPS-5 Arousal and Reactivity (Criterion E).
- Change from baseline in CAPS-5 Intrusion symptoms (Criterion B).
- Change from baseline in CAPS-5 Negative Cognition and Mood (Criterion D).
- Change from baseline in CAPS-5 Persistent Avoidance (Criterion C).
- Change from baseline in CAPS-5 Sleep Disturbance (item E-6).
- Change from baseline in CAPS-5 Exaggerated Startle (item E-4).
- Change from baseline in CAPS-5 Reckless or Self-Destructive Behavior (item E-2).
- Change from baseline in CAPS-5 Depersonalization (item 29).
- Change from baseline in CAPS-5 Derealization (item 30).

The change from baseline in BDI-II score will be analyzed in a Mixed Model Repeated Measures (MMRM) for the change from each baseline (P301 baseline and P303 baseline)

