9.1.2 Categorical outcomes

Binary data over time will be analyzed using a Cochran Mantel Haenszel (CMH) test stratified by presence of current major depressive episode. Participants with missing data will be analyzed as though they are non-responders. This will be reported for each endpoint. Differences in proportions along with two-sided 95% CIs will also be reported. Two-sided p-values for the test of no difference between the treatment groups will be provided.

These endpoints will include:

- Proportion of participants with a CGI-I score of “much improved” or “very much improved”.
- Proportion of participants with a $\geq 50\%$ improvement from baseline in Total CAPS-5 score.

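### A worsening PTSD symptom is an adverse event only if the patient finds it outside normal experience, and no planned table counts patients whose PTSD worsens

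*Protocol*

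**What the plan says.** Protocol 10.3.1 observes that PTSD symptoms fluctuate, then sets the rule for what counts as an adverse event: "Only symptoms that significantly worsen or become more frequent, and in the opinion of the patient are outside of their normal experience, should be reported". The same section says that "AEs that are spontaneously reported, elicited or observed are to be recorded on the CRF". Protocol 11.1 defines an adverse event broadly, to include "any unfavorable and unintended sign (including an abnormal laboratory finding, for example), symptom, or disease temporally associated with the use of a medicinal product". Protocol 12.1 closes by asking that clinically significant abnormalities be recorded as AEs, without saying whether PTSD scale scores are covered.

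On safety measures, Protocol 10.3 states: "Safety will be assessed by evaluation of adverse events, responses on the C-SSRS, clinical laboratory tests, examinations of the oral cavity, vital signs, weight", and adds the BDI-II. CAPS-5 and CGI-I are efficacy measures only.

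In SAP 9.1.1, CAPS-5 is analysed by ANCOVA, where "the dependent variable will be the observed change from each baseline to Week 12", and BDI-II by MMRM on change. SAP 7.2.2 treats CGI-I as continuous from 1 to 7, of which 5, 6 and 7 are grades of worsening. The binary endpoints in SAP 9.1.2 look only upward. One is the "Proportion of participants with a CGI-I score of" much or very much improved. The other is the proportion with at least 50% "improvement from baseline in Total CAPS-5 score".

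**The concern.** The primary objective is safety in patients with PTSD, so deterioration of PTSD on open-label drug is a harm the study should be able to show. The first half of the reporting rule already removes ordinary fluctuation. The second half can also remove a real relapse, because a patient with chronic PTSD who slides back to pre-treatment severity has been there before and may call it normal.

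If the event is not recorded as an AE, the remaining place to see it is the scale data, and no planned analysis of those data counts patients who get worse. By contrast, SAP 10.2 gives each laboratory analysis a shift table from each baseline.

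**Working it through.** The documents state no figure for this point, so the check is mainly textual. The numbers below are illustrations on assumed values.

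**1. The rule as written.** A PTSD symptom is reportable if (A) it significantly worsens or becomes more frequent, and (B) the patient considers it outside normal experience. If A holds and B does not, the rule does not call for a report. No one is named as judge of A; only the patient judges B. This sits badly with the instruction to record observed AEs and with the definition in 11.1, neither of which has a patient-opinion test.

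**2. An invented patient.** CAPS-5 is 40 at lead-in baseline, 10 at P303 entry and 38 at Week 12.
- Change from P303 baseline: 38 - 10 = +28.
- Change from P301 baseline: 38 - 40 = -2.
- Improvement from P301 baseline: (40 - 10)/40 = 75% at entry and (40 - 38)/40 = 5% at Week 12.

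If normal experience means the illness before treatment, B fails and no AE is called for. If it means the state at entry, B holds. The text does not choose.

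**3. Does the newly emergent AE definition catch it?** The Synopsis covers adverse events first reported on open-label drug "or that worsen after entry into the extension study, will be considered newly emergent AEs (NEAEs"). Protocol 11.1 and SAP 10.1 apply the worsening limb to AEs ongoing from the lead-in study. PTSD is the indication, not an ongoing AE, so a symptom stopped by the 10.3.1 rule does not reach this definition.

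**4. Planned outputs.**

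| Measure | Collected | Planned analysis | Count of worsened patients |
|---|---|---|---|
| CAPS-5 | Week 12 or ET | Mean change; at least 50% improvement | None |
| CGI-I | Weeks 4, 8, 12 or ET | Mean of 1-7; proportion scoring 1-2 | None |
| BDI-II | Weeks 4, 8, 12 or ET | Mean change | None |
| C-SSRS | All visits | Counts of ideation and behavior | Suicidality only |

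In the responder tables, missing counts as non-response (SAP 9.1.2), so against the P303 baseline worsened, unchanged and missing patients form one class. SAP 14.1.2 asks that categorical summaries show all categories. That does not commit the SAP to a CGI-I 5-7 count, because CGI-I is handled as continuous or as responder versus non-responder.

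**5. How a mean can hide worsening.** Assume a share r worsens by 15 CAPS-5 points and the rest improve by 3. Mean change = (1 - r)(-3) + r(15) = -3 + 18r. For r = 5%, 10% and 15% this gives -2.1, -1.2 and -0.3. The mean reaches zero only at r = 3/18 = 16.7%.

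**6. Why a threshold matters.** Assume change from the P303 baseline is normal with mean -5.

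| SD | Any rise, 1 - Φ(5/SD) | Rise of 10 or more, 1 - Φ(15/SD) |
|---|---|---|
| 8 | 26.6% | 3.0% |
| 10 | 30.9% | 6.7% |
| 12 | 33.8% | 10.6% |

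Over the same SDs, a rise of 10 or more has probability 5.2% to 13.9% with mean -3, and 1.2% to 6.7% with mean -8.

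**The case against.** The strongest reply is that worsening is far from invisible, and much of that reply stands.

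- **Tables and listings.** SAP 9.1.1 reports SD, median, minimum and maximum for each outcome, and Protocol 12.1 lists all data by patient. A large rise would show as an extreme. A reader might infer that no output would show a relapse at all; these provisions rule that out. They do not say how many patients worsened.
- **Other counted routes.** Treatment-emergent suicidality is counted (Protocol 12.1, SAP 10.3). A significant C-SSRS change is an AE (Protocol 10.3.1.1) and an ideation score of 4 or 5 is an SAE (10.3.1.2). Hospitalization meets the SAE definition (11.3), and withdrawal reasons are tabulated (SAP 8.1). It would be wrong to say that no analysis counts any patient who gets worse. The gap is confined to PTSD symptoms that worsen without these events.
- **Relapsed versus unchanged.** It is tempting to say the two look alike. In the ANCOVA, +28 and 0 contribute differently. Against the P301 baseline, a patient who stays at 10 is a responder and one who returns to 38 is not. They share a class only in the P303-baseline responder table.
- **Dissociation.** Depersonalisation and derealisation are both CAPS-5 items (29 and 30) and abuse-potential terms in SAP Appendix 3, so a reader might infer that the rule keeps them out of the abuse tables. New-onset dissociation would ordinarily be outside the patient's experience and so reportable, and both items are analysed separately in SAP 9.1.1. Only worsening of a pre-existing symptom meets the filter.
- **The filter has a reason.** PTSD symptoms do vary. That supports condition A, but not leaving condition B to the patient alone with no reference period.

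**Conclusion.** The concern holds in this bounded form. Read literally, the rule can leave a real PTSD relapse out of the adverse event tables, and no pre-specified count elsewhere makes up for it. The patients affected are those who return towards pre-treatment severity without suicidality, hospitalization or withdrawal. That a relapse is excluded rests on one plausible reading of an undefined term; the documents do not say it must be.

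The size is unknown. The 27% to 34% in the normal model is the share with any rise above zero, small fluctuation included, and does not estimate a relapse rate. Under the same model, a rise of 28 points has probability 1 - Φ(33/SD), about 0.002%, 0.05% and 0.3% for SD 8, 10 and 12. The means, SDs and relapse shares are all assumed. They show only that a mean improvement is compatible with a minority who worsen materially.

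**What to change.** **Protocol 10.3.1.** Reconcile the rule with the observed-AE instruction in the same section, the definition in 11.1 and the closing sentence of 12.1. Word the second condition as *in the opinion of the patient or the investigator*, and state that the reference is the patient's state at P303 entry.

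**SAP section 10.** Add one descriptive safety table by lead-in arm and overall, from data already collected:
- n (%) with CGI-I 5-7, and with 6-7, versus the P303 baseline, at each visit and at any visit;
- n (%) with CAPS-5 total, and with BDI-II, worse than the P303 baseline by at least a threshold fixed before database lock. Counting any rise above zero would mostly flag noise.

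The CGI-I rows need the rating anchored to the extension baseline, which Protocol 10.2.2 requires. The question text in SAP 7.2.2 is anchored to Visit 2 and should be aligned.

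**Cost.** A short amendment with ethics review, acting only on events recorded afterwards, and one table. AE counts will rise slightly from natural fluctuation. Without a concurrent control, the worsening counts are descriptive and cannot be attributed to the drug.
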